Programmer notes: Clinically significant lab values generally will be captured as AEs, some of which the PI may indicate in Appendix 16.2.8.1.6 lab comments (as per GPG.03.0028 sections 2.9 and 2.10). Derive an additional CS flag for PI flag (+) based on positive comments (i.e. CS/Clinically Significant). Present this derived 4^{th} column in all tables, and list only subjects/tests which are PI-determined clinically significant lab values in Table 14.3.4.5.

```
Note: Treatment A: < >
Treatment B: < >
Treatment C: < >
Treatment D: < >
Treatment P: < >
```

#Age is calculated from the date of first dosing. F = Female, M = Male

H = Above reference range, L = Below reference range

Computer: N = Not clinically significant, Y = Clinically significant

PI Interpretation: - = Not clinically significant, R = Recheck requested, ^ = Will be retested later, + = Clinically significant

Program: /CAXXXX/sas prg/stsas/tab PROGRAMNAME.sas DDMMYYYY HH:MM

Celerion, Clinical Study Report No. CA19214

Page 1 of X

Table 14.3.4.5 Clinically Significant Values and Corresponding Results (Safety Population)

(Cohort	Subject Number		_	Treatment	Day	Hour	Date	Time	Department	Test	Resu	lt 1	Reference Range	Unit
	X	X	XX/X	1	X	X	XX.XX	DDMONYYYY	HH:MM:SS	Serum Chemistry Serum Chemistry	Cholesterol			XX - XX XX - XX	mg/dL mg/dL
						X	XX.XX	DDMONYYYY	HH:MM:SS	Serum Chemistry	Cholesterol	XXX	HYR+	XX - XX	mg/dL

Programmer notes: All time points for a subject/test with at least one value deemed as CS by the PI will be presented in this table.

If no event meets this criteria then include a statement as follows:

```
Note: Treatment A: < >
    Treatment B: < >
    Treatment C: < >
    Treatment D: < >
    Treatment P: < >
    #Age is calculated from the date of first dosing. F = Female, M = Male
    H = Above reference range, L = Below reference range
    Computer: N = Not clinically significant, Y = Clinically significant
    PI Interpretation: - = Not clinically significant, R = Recheck requested, ^ = Will be retested later, + = Clinically significant
```

[&]quot;There were no clinical laboratory results documented as clinically significant by the PI."

Tables 14.3.5.4 (hematology), 14.3.5.7 (urinalysis), and 14.3.5.10 (coagulation & bleeding time) will resemble 14.3.5.1.

Page 1 of X

Table 14.3.5.1 Clinical Laboratory Summary - Serum Chemistry (Safety Population)

	D 6			Treatment						
Laboratory Test (units)	Reference Range	Time Point	Statistic	A	В	С	D	Pooled Placebo		
Testname (unit)	< - >#	Screen	n	X	X	X	X	X		
			Mean	X.X*	X.X	X.X	X.X	X.X		
			SD	X.XX	X.XX	X.XX	X.XX	X.XX		
			Minimum	XX	XX	XX	XX	XX		
			Median	X.X	X.X	X.X	X.X	X.X		
			Maximum	XX	XX	XX	XX	XX		
		Baseline	n	X	X	X	X	X		
			Mean	XX.XX	XX.XX	XX.XX*	XX.XX	XX.XX		
			SD	X.XXX	X.XXX	X.XXX	X.XXX	X.XXX		
			Minimum	XX.X	XX.X	XX.X	XX.X	XX.X		
			Median	XX.XX	XX.XX	XX.XX	XX.XX	XX.XX		
			Maximum	XX.X	XX.X	XX.X	XX.X	XX.X		

Programmer note: Time points are Screen, Baseline, Day 1 Hour 8, Day 2, Day 8, Day 29, and Follow-up. Coagulation time points are Screen, Baseline, Day 1 Hour 1, Day 2, Day 4, Day 8, Day 29, and Follow-up. aPTT samples for PD time points are not presented here. Bleeding time is presented with coagulation with time points Check-in, Baseline, Day 1 Hour 1, and Day 2.

Programmer note: Treatment means at specific time points will be flagged (with a *) if they are above or below the reference range. This only applies to the clinical laboratory treatment results (i.e., not the change from baseline or any other endpoints).

Programmer note: The following footnote only presented on Coagulation summary tables

Summaries for aPTT associated with PD time points can be found in Table

14.X.X.X.

Note: Treatment A: < >

Treatment B: < >

Treatment C: < >

Treatment D: < >

Baseline is the last predose measurement.

= Lowest of the lower ranges and highest of the higher ranges are used. Refer to Appendix 16.1.10.1 for the breakdown.

*Outside reference range

Tables 14.3.5.5 (hematology), 14.3.5.8 (urinalysis), and 14.3.5.11 (coagulation & bleeding time) will resemble 14.3.5.2.

Table 14.3.5.2 Clinical Laboratory Change From Baseline - Serum Chemistry (Safety Population)

					Treatmen	ıt	
Laboratory Test (units)	Time Point	Statistic	A	В	С	D	Pooled Placebo
Testname (unit)	Day 1 Hour 8	n	X	X	X	X	X
		Mean	X.X	X.X	X.X	X.X	X.X
		SD	X.XX	X.XX	X.XX	X.XX	X.XX
		Minimum	XX	XX	XX	XX	XX
		Median	X.X	X.X	X.X	X.X	X.X
		Maximum	XX	XX	XX	XX	XX
	Day 2	n	X	X	X	Х	X
		Mean	XX.XX	XX.XX	XX.XX	XX.XX	XX.XX
		SD	X.XXX	X.XXX	X.XXX	X.XXX	X.XXX
		Minimum	XX.X	XX.X	XX.X	XX.X	XX.X
		Median	XX.XX	XX.XX	XX.XX	XX.XX	XX.XX
		Maximum	XX.X	XX.X	XX.X	XX.X	XX.X

Programmer note: Time points are Day 1 Hour 8, Day 2, Day 8, Day 29, and Follow-up. Coagulation time points are Day 1 Hour 1, Day 2, Day 4, Day 8, Day 29, and Follow-up. aPTT samples for PD time points are not presented here. Bleeding time is presented with coagulation with time points Day 1 Hour 1 and Day 2.

Programmer note: The following footnote only presented on Coagulation summary tables

Change from baseline summaries for aPTT associated with PD time points can be found Table 14.X.X.X.

Note: Treatment A: < >
Treatment B: < >
Treatment C: < >
Treatment D: < >

Baseline is the last predose measurement.

Program: /CAXXXXX/ECR/sas prg/stsas/tab programname.sas DDMMMYYYY HH:MM

Page 1 of X

Tables 14.3.5.6 (hematology), 14.3.5.9 (urinalysis), and 14.3.5.12 (coagulation & bleeding time) will resemble 14.3.5.3

Page 1 of X Table 14.3.5.3 Clinical Laboratory Shift From Baseline - Serum Chemistry (Safety Population)

			Baseline L		Baseline N		Bas	eline	Н		
		_		Postdo	se	Po	stdos	е		Postdo	ose
Laboratory Test (units)	Treatment	Time Point	L	N	Н	L	N	Н	L	N	Н
Testname (unit)	Х	Day 1 Hour 8	Х	XX	X	X	XX	Х	Х	XX	Х
		Day 2	X	XX	X	X	XX	X	X	XX	X
		Day 8	Χ	XX	X	X	XX	X	X	XX	X
		Day 29	X	XX	X	X	XX	X	X	XX	X
		Follow-up	Χ	XX	X	X	XX	X	X	XX	X
Testname (unit)	X	Day 1 Hour 8	Х	XX	X	Х	XX	X	X	XX	X
		Day 2	Χ	XX	X	X	XX	X	X	XX	X
		Day 8	Χ	XX	X	X	XX	X	X	XX	X
		Day 29	Χ	XX	X	X	XX	X	X	XX	X
		Follow-up	X	XX	X	X	XX	X	X	XX	Χ

Programmer note: Time points are Day 1 Hour 8, Day 2, Day 8, Day 29, and Follow-up. Coagulation time points are Day 1 Hour 1, Day 2, Day 4, Day 8, Day 29, and Follow-up. aPTT samples for PD time points are not presented here. Bleeding time is presented with coagulation with time points Day 1 Hour 1 and Day 2.

Programmer note: For urinalysis, the following footnote is used since the categories of N and O will be used instead of L, N, and H

Note: N = Within reference range, O = Outside reference range

Note: Treatment A: < >
Treatment B: < >

Treatment C: < >

Treatment D: < >

 ${\tt N}$ = Within reference range, L = Below reference range, H = Above reference range Baseline is the last predose measurement.

Change From Baseline Table 14.3.5.14 will resemble 14.3.5.13

Table 14.3.5.13 Vital Sign Summary (Safety Population)

Page 1 of X

	Time Point		Treatment							
Vital Sign (units)		Statistic	А	В	C	D	Pooled Placebo			
Testname (unit)	Screen	n	X	X	X	Х	X			
		Mean	X.X	X.X	X.X	X.X	X.X			
		SD	X.XX	X.XX	X.XX	X.XX	X.XX			
		Minimum	XX	XX	XX	XX	XX			
		Median	X.X	X.X	X.X	X.X	X.X			
		Maximum	XX	XX	XX	XX	XX			
	Baseline	n	X	Х	X	X	X			
		Mean	X.X	X.X	X.X	X.X	X.X			
		SD	X.XX	X.XX	X.XX	X.XX	X.XX			
		Minimum	XX	XX	XX	XX	XX			
		Median	X.X	X.X	X.X	X.X	X.X			
		Maximum	XX	XX	XX	XX	XX			
	Day 1 Hour 0.	25 n	X	X	X	X	X			
	_	Mean	X.X	X.X	X.X	X.X	X.X			
		SD	X.XX	X.XX	X.XX	X.XX	X.XX			
		Minimum	XX	XX	XX	XX	XX			
		Median	X.X	X.X	X.X	X.X	X.X			
		Maximum	XX	XX	XX	XX	XX			

Programmer note: Time points are Screen, Baseline, Day 1 Hour 0.25, Day 8, Day 29, and Follow-up.

Note: Treatment A: < >
 Treatment B: < >
 Treatment C: < >
 Treatment D: < >

Baseline is the last predose measurement.

Change From Baseline Table 14.3.5.16 will resemble 14.3.5.15

Page 1 of X

Table 14.3.5.15 12-Lead Electrocardiogram Summary (Safety Population)

			Treatment							
Measurement (units) Time	Point	Statistic	А	А В		D	Pooled Placebo			
Testname (unit) Scre	en	n	X	Х	X	Х	X			
		Mean	X.X	X.X	X.X	Х.Х	X.X			
		SD	X.XX	X.XX	X.XX	X.XX	X.XX			
		Minimum	XX	XX	XX	XX	XX			
		Median	X.X	X.X	X.X	X.X	X.X			
		Maximum	XX	XX	XX	XX	XX			
Base	line	n	X	Х	X	X	Х			
		Mean	X.X	X.X	X.X	X.X	X.X			
		SD	X.XX	X.XX	X.XX	X.XX	X.XX			
		Minimum	XX	XX	XX	XX	XX			
		Median	X.X	X.X	X.X	X.X	X.X			
		Maximum	XX	XX	XX	XX	XX			
Day	1 Hour 0.25	n	X	X	X	X	X			
		Mean	X.X	X.X	X.X	X.X	X.X			
		SD	X.XX	X.XX	X.XX	X.XX	X.XX			
		Minimum	XX	XX	XX	XX	XX			
		Median	X.X	X . X	X.X	X.X	X.X			
		Maximum	XX	XX	XX	XX	XX			

Programmer note: Time points are Screen, Baseline, Day 1 Hour 0.25, Day 8, Day 29, and Follow-up.

Note: Treatment A: < >
Treatment B: < >
Treatment C: < >
Treatment D: < >

Baseline is the last predose measurement.

Table 14.3.5.17 ADA Detection Summary by Collection Time and Treatment (Safety Population)

				Treatm	Treatment					
Time Point	Assay Type		- - A			D	Pooled Placeb			
Predose	Screening	Negative Positive	X X	X X	X X	X X	X X			
	Confirmatory	Negative Positive	X X	X X	X X	X X	X X			
Day 15	Screening	-	Х	X	X	Х	X			
	Confirmatory	Positive Negative Positive	X X X	X X X	X X X	X X X	X X X			
Day 29	Screening		X	X	X	X	X			
	Confirmatory	Positive Negative Positive	X X X	X X X	X X X	X X X	X X X			
Follow-up	Screening	Negative	X	X	X	X	X			
	Confirmatory	_	X X	X X	X X	X	X X			
Overall*	Screening	Positive Negative	X	X X	X X	X	X X			
	Confirmatory	Positive Negative		X X	X X	X X	X X			
		Positive	X	X	X	X	X			

Note: Follow-up ADA detection sample only collected if Follow-up visit occurred after Day 36.

*For overall counts, if the response of a subject is positive at least once, the subject will be counted as positive; otherwise, the subject will be considered negative.

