- l: aPTT and free xisomab 3G3 blood samples will be collected for at least 672 hours and until aPTT values return within  $\pm 10\%$  of baseline value or the normal range. If by Day 29, aPTT has not returned to baseline or normal range, sampling will continue every 7 days ( $\pm 2$  days) until the  $\pm 10\%$  of baseline value or the normal range was reached or, as per PI discretion, a maximum of  $\sim 500$  mL of blood was collected from the subject. Subjects who terminate the study early will return every 7 days ( $\pm 2$  days) for aPTT monitoring until aPTT values return within  $\pm 10\%$  of baseline value or the normal range.
- m: An additional ADA sample will be collected at the FU visit only in the event that the FU visit occurs after Day 36.

Abbreviations: ADA = anti-drug antibodies, aPTT = Activated partial thromboplastin time, BP = Blood pressure, C-I = Check-in, Chem = Chemistry, CRU = Clinical research unit, FSH = Follicle-stimulating hormone, FU = Follow-up, Hem = Hematology, HIV = Human immunodeficiency virus, HR = Heart rate, INR = International normalized ratio, PD = Pharmacodynamic, PI = Principal Investigator, PK = Pharmacokinetics, PT = Prothrombin time, RR = Respiratory rate, T = Temperature, UA = Urinalysis.

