## 8.5 Risk/Benefit

The safety monitoring practices employed by this protocol (e.g., physical examination, vital signs, 12-lead ECG, hematology, serum chemistry, urinalysis, coagulation, injection site reaction monitoring, and AE questioning) are adequate to protect the subjects' safety and should detect all expected TEAEs.

As there is a potential to develop an immune response to a biologic agent, immunogenicity will be assessed in this study.

The approximate volume of blood planned for collection from each subject over the course of the study (see [Section 11.4](#)), presents no undue risk to the subjects nor does the possibility of collection (for wasting to ensure clean sample) of additional blood in the event an indwelling cannula is utilized and the possibility of additional blood for recheck of safety labs if deemed necessary by the PI or designee.

There will be no direct health benefit for trial participants from receipt of study drug. An indirect health benefit to the healthy subjects enrolled in this trial is the free medical tests received at screening and during the study.

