2.2 Endpoints

The primary endpoints of the study will be the number and severity of treatmentemergent adverse events (TEAEs) following single doses of xisomab 3G3 and placebo. Other safety endpoints include clinical laboratories, vital signs, electrocardiograms, physical examinations, and immunogenicity.

- The following PK parameters of free xisomab 3G3 in plasma following single IV dose, will be calculated, as appropriate: AUC0-t, AUC0-inf, AUC%extrap, Cmax, Tmax, Kel, T½, MRT, CL, and Vss.
- aPTT values will be listed with descriptive statistics and presented graphically.

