8. SAFETY

No inferential statistics will be performed on safety data.

All case report form (CRF) data will be listed by subject and chronologically by assessment time points. This will include rechecks, unscheduled assessments, and early termination.

Applicable continuous variables will be summarized using n, arithmetic mean, SD, minimum, median, and maximum. Data from subjects who received the placebo treatment will be pooled across cohorts.

The level of precision will be presented as follows: minimum/maximum in the same precision as in the database, mean/median in one more precision level than minimum/maximum, SD in one more precision level than mean/median, and n will be presented as an integer.

Where individual data points are missing because of dropouts or other reasons, the data will be summarized based on reduced denominators.

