8.3 Adverse Events and Injection Site Reaction

All adverse events (AEs) occurring during this clinical trial will be coded using the Medical Dictionary for Regulatory Activities (MedDRA®), Version 20.0.

All AEs captured in the database will be listed in by-subject data listings including verbatim term, coded term, treatment, severity, relationship to study drug, and action; however, only treatment-emergent AEs (TEAEs) will be summarized.

A TEAE is defined as an AE that is starting or worsening at the start time of study drug administration or after. Each TEAE will be attributed to a treatment based on the onset date and time of the AE.

If an AE increases in severity, that AE will be given a resolution date and time and a new record will be initiated with the new severity. If the severity of an AE remains the same or decreases, the AE will be kept open through to resolution.

If the onset time of an AE is missing and the onset date is the same as the treatment dosing date or after the treatment dosing date, then the AE will be considered treatment emergent. If the onset date of an AE is missing, then the AE will be considered treatment emergent.

TEAEs will be tabulated by System Organ Class (SOC) and Preferred Term. Summary tables will include number of subjects reporting the AE and as percent of number of subjects dosed by treatment (pool placebo and xisomab 3G3 dose levels) and pooled active (xisomab 3G3 doses pooled). The number of AEs will be tabulated in a similar manner. Tables which tabulate the number of TEAEs by severity and relationship to study treatment will also be included.

Injection site reaction will be assessed and any abnormal finding will be reported as an adverse event.

Serious adverse events (SAEs), if present, will also be listed. Applicable narratives will be included in the CSR.

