All coagulation results for PD endpoint aPTT will be listed with the clinical laboratory results and included in the out-of-range table, but for the time points outlined in Section 7.1 summaries will not be included in the clinical laboratory summary tables.

For all numeric laboratory values, descriptive statistics will be presented for each laboratory test by assessment time point and treatment (pooled placebo and xisomab 3G3 dose levels). Change from baseline will be summarized in a similar manner. Baseline is defined as the result closest and prior to dose which may include unscheduled or recheck results. This will typically be the result collected on Day -1.

Postdose unscheduled events or rechecks will not be included in summaries. Similarly early termination results will not be included in summaries.

For each laboratory test, a shift table will be developed to compare the frequency of the results at baseline (above normal, normal, or below normal) with the respective postdose results. For urinalysis tests, the categories are normal and outside normal.

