8.10 Immunogenicity

Blood samples will be collected from each subject for ADA detection at predose, Day 15, Day 29, and at the Follow-up visit only in the event that the Follow-up visit occurs after Day 36. Immunogenicity testing will be done at Celerion, Lincoln, Nebraska.

A qualitative screening assay will be performed on all samples and results reported as positive or negative for ADA detection. If the screening assay is positive, a qualitative confirmatory assay will be performed on the sample to confirm that the antibodies are specific to xisomab 3G3, with results reported as positive or negative. Confirmed positive samples for ADA will be reassayed, at a series of 2-fold dilutions prior to analysis. The greatest dilution that results in a mean response greater than the assay cut point will be reported as the titer for that sample.

On the other hand, if the screening result is negative, confirmatory and titer assays will not be performed. In the case where the confirmatory result is negative, but the screening result was positive, the titer assay will not be performed.

Results from the qualitative screening and confirmatory ADA detections will be listed as positive or negative. For samples with a positive confirmatory assay, a titer value will be presented with the same level of precision as received from the bioanalytical laboratory.

Frequency counts of positive and negative ADA detection will be presented by collection time, assay type (screening or confirmatory) and treatment (pooled placebo and xisomab 3G3 dose levels).

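### The Overall row of SAP Table 14.3.5.17 counts predose ADA positives, and no row gives the across-visit number of subjects newly positive after dosing

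*SAP*

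**What the plan says.** SAP 8.10 schedules ADA samples "at predose, Day 15, Day 29, and at the Follow-up visit only in the event that the Follow-up visit occurs after Day 36". Footnote m of the Protocol Section 6 flow chart puts the same condition on the last sample: "An additional ADA sample will be collected at the FU visit only in the event that the FU visit occurs after Day 36". SAP 8.10 plans frequency counts of positive and negative results by collection time, assay type and treatment.

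The shell of Table 14.3.5.17 (SAP 11.3) has rows for Predose, Day 15, Day 29, Follow-up and Overall, each split into screening and confirmatory results. The Overall footnote says: "For overall counts, if the response of a subject is positive at least once, the subject will be counted as positive". All other subjects are counted as negative.

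SAP 2.2 makes immunogenicity a safety endpoint: "Other safety endpoints include clinical laboratories, vital signs, electrocardiograms, physical examinations, and immunogenicity". Protocol 8.5 gives the reason for measuring it: "As there is a potential to develop an immune response to a biologic agent, immunogenicity will be assessed in this study". Neither document defines treatment-emergent ADA or any count that pools the post-dose visits.

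**The concern.** The reason given in Protocol 8.5 is that the drug may provoke an immune response. An across-visit count that answers this has to separate antibodies present before dosing from those that appear afterwards. The Overall row is the only across-visit subject count in the only ADA summary table that the SAP lists, and it mixes the two.

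Elsewhere the SAP makes the separation. For adverse events: "A TEAE is defined as an AE that is starting or worsening at the start time of study drug administration or after". For laboratory tests, "a shift table will be developed to compare the frequency of the results at baseline" with the post-dose results. ADA also has a predose sample but gets neither treatment.

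At stake is how one row of a safety table is read. With so few subjects per group, a single pre-existing or false-positive predose result decides whether a dose level shows no positives or one.

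**Working it through.** **Inputs.** Four active subjects at each dose level (SAP Section 5). Pooled placebo is 2 + 1 + 1 + 1 = 5. Visits and the Overall rule are as in the Table 14.3.5.17 shell. The plan states no figure to reproduce. Neither document gives a predose positivity rate.

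**Step 1: one subject positive at predose only.** The rows for that group read Predose 1, Day 15 0, Day 29 0, Overall 1.
- Overall as written: 1/4 at a dose level, or 1/5 in pooled placebo.
- Count from post-dose samples only: 0/4, or 0/5.

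**Step 2: can newly positive subjects be recovered?** With complete predose results, every Overall-positive subject is either positive at predose, or negative at predose and positive later. Therefore

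Overall = Predose positives + newly positive, so newly positive = Overall − Predose.

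This is exact. Enumerating every positive/negative pattern for 4 subjects, with complete Predose, Day 15 and Day 29 results and k of the 4 also sampled at Follow-up, found no exception.

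**Step 3: what cannot always be recovered.** The same enumeration gives the number of distinct sets of row counts (tables), and how many of them fit more than one value of a given quantity:

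| k sampled at Follow-up | Possible tables | Any-post-dose count ambiguous | Newly positive by Day 29 ambiguous | Of the latter, no predose positive |
|---|---|---|---|---|
| 0 | 190 | 45 | 0 | 0 |
| 1 | 399 | 126 | 65 | 10 |
| 2 | 610 | 208 | 140 | 23 |
| 3 | 798 | 268 | 214 | 36 |
| 4 | 923 | 268 | 268 | 45 |

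- *Any post-dose positive.* Every ambiguous table has at least one predose positive, so this ambiguity does need predose positives in Overall. Example with k = 0: Predose 1, Day 15 1, Day 29 1, Overall 2. If A is positive at predose only and B at Day 15 and Day 29, one subject is positive after dosing. If A is positive at predose and Day 15 and B at Day 29, two are.
- *Newly positive by Day 29.* With no Follow-up samples, subtraction is exact. Once Follow-up samples enter Overall it may not be, and part of this has nothing to do with Predose. Example with one Follow-up sample: Predose 0, Day 15 1, Day 29 1, Follow-up 1, Overall 2 fits either one or two subjects newly positive by Day 29. The cause there is the pooling of a conditional visit.

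These are shares of possible tables, not probabilities.

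**Step 4: missing post-dose samples.** Under the footnote, a predose-negative subject with no post-dose sample is counted as an Overall negative. SAP Section 8 says of missing data that "the data will be summarized based on reduced denominators". The footnote does not say which rule applies to the Overall row.

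**The case against.** The strongest reply is that the table hardly misleads. Predose has its own row, so in the Step 1 case the reader sees Predose 1, nothing at Day 15 or Day 29, and Overall 1. Ever-positive is a legitimate descriptive count, and the footnote states it openly. Newly positive subjects follow by subtraction, and listing 16.2.8.4 gives each subject's screening, confirmatory and titer results for a planned total of 21 subjects. Subjects who stop early are asked to return for the Day 15 and Day 29 ADA samples, so missing post-dose results should be few. SAP Section 11 says the shells may change. All of this stands, and it limits the severity. It does not give the plan a prespecified count of subjects who became positive after dosing.

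Three stronger readings are not supported:
- A reader might infer that the table contains no post-dose counts. It does: the Day 15, Day 29 and Follow-up rows count post-dose positives visit by visit. Only an across-visit count is missing.
- A reader might infer that the SAP contradicts itself or presents pre-existing antibodies as drug-induced. The Overall row is not labelled treatment-emergent.
- A reader might attribute all of the Day 29 ambiguity to the inclusion of Predose. The last column of the table shows that some of it arises with no predose positive at all.

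**Conclusion.** The point holds, at low severity. As written, one predose-only positive moves Overall from 0/4 to 1/4 at a dose level, or from 0/5 to 1/5 in pooled placebo. No planned row states how many subjects became positive after dosing.

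The consequence is confined to presentation. The analysis is descriptive, the table is post-text with no in-text counterpart (SAP 10.1), and neither stopping trigger in Protocol 10.4.1.4 uses ADA.

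The conclusion rests on reading the footnote as covering every time point in the table, which is its plain meaning. The subtraction result assumes complete predose data. How often a predose positive would occur is unknown. If there were none, Overall would already equal the any-post-dose count.

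**What to change.** 1. Add one row to Table 14.3.5.17, on confirmed results, for treatment-emergent ADA: not confirmed positive at predose, and confirmed positive at any post-dose sample. Use subjects with at least one post-dose ADA result as the denominator.
2. Either keep Overall and label it 'ever positive, including predose', or restrict it to post-dose samples. Restriction alone is not enough: a subject positive before dosing and unchanged afterwards would still count as Overall-positive, and the subtraction in Step 2 would no longer work. The added row is needed either way.
3. Show the treatment-emergent count through Day 29 as well, since those samples are scheduled for all subjects. This deals with the pooling of the conditional Follow-up sample, not with the inclusion of Predose.

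The cost is a footnote and one or two rows in one SAP shell. The predose sample and the confirmatory assay are already planned, and trial conduct does not change. The downside is a slightly smaller denominator if post-dose samples are missing.
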